### ***Daily Patient Assessment of Abdominal Pain at its Worst***

Patient assessment of abdominal pain at its worst will be collected via a daily evening report in the eDiary. The rating of abdominal pain at its worst during the previous 24 hours on an 11-point numerical rating scale (NRS) will be provided by the patient answering the following question:

“How would you rate your worst abdominal pain in the past 24 hours?”

<eDiary presents NRS where 0 is anchored with “No abdominal pain” and 10 is anchored with “Worst possible abdominal pain”>

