#### **Weekly Change from Baseline in Abdominal Pain**

Abdominal pain is measured daily using an 11-point NRS. A patient's weekly abdominal pain score is the average of the nonmissing abdominal pain scores reported by the patient during each week.

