### 9.2 VISIT TIME WINDOWS FOR EFFICACY ANALYSIS

Table 6 presents the analysis weeks assigned for the efficacy analysis of the patient diary data related to BM characteristics. These analysis weeks will be used in the calculations for all week-based parameters (e.g., SBM weekly frequency rate, BSFS weekly scores).

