**Table 6. Analysis Time Windows for Efficacy Analysis**

Period	Analysis Week	Begins a	Ends a
Pretreatment (Baseline b )	Week -2	Day -14	Day -8
	Week -1	Day -7	Day 1 (time of randomization)
Treatment	Week 1	Day 1 (time of randomization)	Day 7
	Week 2	Day 8	Day 14
	Week 3	Day 15	Day 21
	Week 4	Day 22	Day 28
	Week 5	Day 29	Day 35
	Week 6	Day 36	Day 42
	Week 7	Day 43	Day 49
	Week 8	Day 50	Day 56
	Week 9	Day 57	Day 63
	Week 10	Day 64	Day 70
	Week 11	Day 71	Day 77
Week 12	Day 78	last dose day c (usually Day 85)	

Note: There is no Day 0 or Week 0. For eDiary assessments in which a patient is asked to report if an event occurred “yesterday” or “today” (e.g., a bowel movement or rescue medication use), these windows pertain to when the event occurred, not to when the event is reported. For example, if a patient reports in eDiary on Day 78 a bowel movement occurring “yesterday,” that bowel movement (and subsequent stool consistency and straining scores) would be included in Analysis Week 11, not Analysis Week 12.

- Relative to the date of randomization; Day 1 = the day of randomization. For the calculation of rates (e.g., stool frequency rates) in which the duration of a week or the overall period is calculated to the nearest hour, a day begins and ends at midnight.
- Baseline values for efficacy parameters will be derived from the daily eDiary and eCRF data collected in the Pretreatment Period, specifically the period from 14 days before randomization up to the time of randomization.
- For patients who fail to provide the date of last dose at the last visit, the last eDiary date will be used to impute the last dose date.

For the Treatment Period, diary day is calculated as diary date – date of randomization + 1. For the Pretreatment Period, diary day is calculated as diary date - date of randomization. However, the day of randomization is always trial Day 1. Patients will complete their diary entries once a day, with the exception of Day 1 of entry into the Treatment Period during which 2 diary data sets will be collected. On Day 1, daily questions will be entered before and after the randomization, whereas weekly questions will be entered before but not after randomization.

If a patient withdraws during the Treatment Period, the patient’s Treatment Period shall end on the day of the last dose. The affected Treatment Period week shall be shortened to the end of the

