### **Abdominal Symptom Severity**

During the Evening Diary Report, the eDiary will capture separately the rating of abdominal pain, bloating, and discomfort experienced by the patient during the past 24 hours.

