#### 9.4.4 Other Weekly Scores Derivation

For Abdominal Pain, Bloating, and Discomfort, the patient's weekly average will be the average of the non-missing daily scores reported by the patient during each week.

For stool consistency questions, the patient's weekly score will be the average of the non-missing daily scores from the SBMs reported by the patient during each week.

For straining, the patient's weekly straining score will be the average of the non-missing daily straining scores from the SBMs reported by the patient during each week.

For the abdominal symptom composite score, first the daily average of Abdominal Pain, Abdominal Bloating and Abdominal Discomfort will be calculated. If more than 1 of the symptom scores is missing on a day, that daily abdominal symptom composite score will be missing. Weekly scores will be based on the average of the non-missing abdominal symptom composite scores.

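### The Day 1 evening rating of worst pain in the past 24 hours always reaches back before the first dose, yet it is averaged into treatment Week 1 and pulls the Week 1 pain estimate modestly toward zero.

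*SAP*

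**What the plan says.** - **How pain is rated.** SAP 5.3.1: "Patient assessment of abdominal pain at its worst will be collected via a daily evening report in the eDiary." The item reads "How would you rate your worst abdominal pain in the past 24 hours". SAP 9.4.1 confirms the recall period for all three abdominal symptoms: "the eDiary will capture separately the rating of abdominal pain, bloating, and discomfort experienced by the patient during the past 24 hours."
- **Day 1.** The text under SAP Table 6: "On Day 1, daily questions will be entered before and after the randomization, whereas weekly questions will be entered before but not after randomization." In Protocol 5.5.1 (Randomization Visit) the abdominal ratings are among the clinic entries made before randomization. Patients are then told to keep using the eDiary for the rest of that day.
- **Windows.** In Table 6 the baseline period ends, and Week 1 begins, at the time of randomization on Day 1. SAP 9.2 says of these weeks: "These analysis weeks will be used in the calculations for all week-based parameters."
- **Weekly score.** SAP 7.9.1: "A patient's weekly abdominal pain score is the average of the nonmissing abdominal pain scores reported by the patient during each week." SAP 9.4.4 repeats the rule for pain, bloating and discomfort: the "weekly average will be the average of the non-missing daily scores reported by the patient during each week."
- **First dose.** It is given in clinic at the Randomization Visit, after the pre-randomization diary entry (Protocol 5.5.1; note n to SAP Table 2).
- **Use.** Weekly change in abdominal pain is the first key parameter, and SAP 7.9.1.1 compares treatments with placebo at each week.

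**The concern.** The rating made on the evening of Day 1 is a treatment rating by its date but only partly by its content. Its 24 hours include the hours before the first dose, and some of those may already have been rated in the clinic entry that belongs to baseline. Because the item asks for the worst pain, a pre-dose peak can set the whole score.

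The SAP avoids this for other diary items. The note to Table 6 assigns bowel movements and rescue use by when they happened, not when they were reported, and the weekly questions are not asked again after randomization. The occurrence rule covers only items asked as today or yesterday, so the 24-hour abdominal ratings fall outside it. No other rule removes or reassigns the Day 1 evening rating.

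At stake are the Week 1 estimates for pain, discomfort, bloating and the composite, and Week 1 status for the pain, abdominal symptom score and APC +1 responders.

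**Working it through.** **1. The plan's own figures (SAP section 4).** Inputs: means -1.196, -1.586, -1.975, -1.975; SD 1.73; 65 per arm; two-sided 0.05.
- Trend: contrast (-3, -1, 1, 3) gives L = -2.726. SE = 1.73 × √(20/65) = 0.960. Power = Φ(2.726/0.960 - 1.96) = 81.1%, against 81% stated.
- Pairwise: difference 0.779, SE = 1.73 × √(2/65) = 0.303. Power = Φ(0.779/0.303 - 1.96) = 72.8%, against 73% stated.

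**2. Pre-dose share of the recall window, f.** The documents give no dosing or report time. The only clock cue is the 7:00 PM recall boundary in SAP 9.4.1. Assume a dose from 8 AM to 2 PM and a report from 7 to 11 PM, with f = (24 - hours from dose to report)/24.
- Lowest: dose 8 AM, report 11 PM: 9/24 = 38%.
- Highest: dose 2 PM, report 7 PM: 19/24 = 79%.

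**3. Attenuation of the Week 1 difference.** Treat the Day 1 rating as a mixture, with share f at baseline level and the rest at full effect. With k ratings averaged, the loss is f/k.

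| Ratings in Week 1 | f = 38% | f = 79% | f = 100% |
|---|---|---|---|
| 7 | 5% | 11% | 14% |
| 4, including Day 1 | 9% | 20% | 25% |

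The mixture is an approximation. A worst-pain score can follow a pre-dose peak even when few of the hours are pre-dose, which is why f = 100% is kept as the upper bound.

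**4. Twelve-week effect.** One of about 84 ratings: 1/84 = 1.2% at most.

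**5. Week 1 pain responder.** If the Day 1 rating equals baseline, the other six must average a fall of 0.30 × 7/6 = 35% for the week to reach 30%. With four ratings in all it is 0.30 × 4/3 = 40%.

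**6. Power at Week 1.** The documents give no Week 1 effect or SD, so borrow 0.779 and 1.73 for the Days 2-7 mean, and assume a daily within-patient SD of 1.4 and 15 baseline ratings.
- Between-patient variance of true change: 1.73² - 1.96/6 - 1.96/15 = 2.993 - 0.327 - 0.131 = 2.536.
- With a wholly baseline-like Day 1 rating included: effect 0.779 × 6/7 = 0.668; variance (6/7)² × 2.536 + 1.96/7 + 1.96/15 = 1.863 + 0.280 + 0.131 = 2.274; SD 1.51.
- Standardized effect: 0.779/1.73 = 0.450 without the rating and 0.668/1.508 = 0.443 with it. Pairwise power is 72.8% and 71.4%, a loss of about 1 point in the worst case.

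**The case against.** The strongest reply is that this is a convention with little consequence. The Treatment Period begins with treatment assignment (Protocol 5.1.1.3), and Table 6 follows that. The distortion acts in every arm and toward zero, so it favours no dose and creates no false positive. The test tied to the primary objective is the overall dose trend across 12 weeks, and the week-by-week p-values are nominal. All of this stands, and it limits the point to the Week 1 estimates and Week 1 responder status.

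Four stronger readings are tempting, and the documents do not support them.
- **A large power loss.** Shrinking the effect while holding the SD at 1.73 gives about 65% at f = 58% and 59% at f = 100%. But a baseline-like rating shrinks each patient's change as well, so the SD falls with the effect (step 6).
- **Mostly pre-dose recall.** More than half the window is pre-dose only if the dose comes less than 12 hours before the report. An early dose with a late report fails that test, and no clock times are given.
- **A responder rule stricter than stated.** The rule is defined on the scores reported in the week and is applied exactly so. The 35% figure describes what that rule demands of Days 2-7 for one kind of patient.
- **Week 1 as the onset measure.** The visible text defines no pain-onset endpoint. The only early-onset efficacy parameter is a CSBM or SBM within 24 hours of first dose (SAP 7.9.2), which uses event times and is unaffected.

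**Conclusion.** The point holds as a modest attenuation of the Week 1 estimate. By the SAP's own rules the post-randomization Day 1 rating enters Week 1, and its recall window always includes pre-dose hours. Under the assumed clock times the Week 1 pain difference is understated by about 5-11% with seven ratings, 14% if the rating is wholly baseline-like, and more with fewer ratings. The direction is toward zero in every arm.

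Power at Week 1 is nearly unchanged, and the 12-week trend analysis is essentially unaffected. That every window contains some pre-dose time follows from the documents. The percentages rest on the assumed clock times and the mixture approximation, and the power comparison rests on borrowed 12-week inputs and an assumed daily SD. This is a cheap improvement to a key parameter's weekly estimate and does not threaten the trial's main conclusion.

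**What to change.** In SAP 9.2 and 9.4.4, state that the Week 1 and 12-week averages of the 24-hour recall items (pain, discomfort, bloating and the composite) start with the Day 2 evening report, and that the post-randomization Day 1 rating is listed only.

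The same text must settle the completeness rule. For the pain, abdominal symptom score and APC responder definitions, the Week 1 minimum of four complete evening reports should be counted on Days 2-7. Otherwise a Week 1 pain mean could rest on three ratings. Leave the bowel movement and rescue medicine windows as they are.

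Cost: a short SAP addition and a programming condition, to be set before unblinding. Week 1 then has at most six ratings, and slightly more patients may miss the four-report minimum that week.

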### 9.3 POOLING OF TRIAL CENTERS

Because of the potential of many trial centers to have a small number of patients, the centers will be pooled by the following 5 geographic regions (as listed in [Table 7](#)): Northeast, Southeast, Midwest, Southwest, and West. All analyses using trial center will use this 5-category center variable.

**Table 7. Definition of Geographic Regions**

Northeast	Southeast	Midwest	Southwest	West
CT	AL	IA	AZ	CA
DE	AR	IL	NM	CO
MA	FL	IN	OK	ID
MD	GA	KS	TX	MT
ME	KY	MI		NV
NH	LA	MN		OR
NJ	MS	MO		UT
NY	NC	ND		WA
PA	SC	NE		WY
RI	TN	OH		
VT	VA	SD		
	WV	WI		

### 9.4 DERIVED EFFICACY VARIABLES

#### 9.4.1 Patient Recall for eDiary Data

##### Bowel Habits

The eDiary is designed to allow patients to enter Daily Bowel Habits through a spontaneous report or the evening report.

The spontaneous report allows the patient to report BMs, occurring between evening reports, at any time. If the previous evening report was not completed, then the patient can report BM information occurring between 7:00 PM of the previous night and the current spontaneous report.

The evening report allows the patient to report BM information between the time of the previous evening report and the current evening report (~24-hour recall). If the previous evening report was not completed, then the patient can report BM information within the evening report occurring between 7:00 PM of the previous night and the current evening report.

These BM information reporting rules were put into place to reduce recall bias.

### **Rescue Medicine (RM)**

The spontaneous report allows the patient to report RM information, occurring between evening reports, at any time. If the previous evening report was not completed, then the patient can report RM information between 7:00 PM of the previous night and the current spontaneous report.

The evening report allows the patient to report RM information between the time of the previous evening report and the current evening report (~24-hour recall). If the previous evening report was not completed, then the patient can report RM information within the evening report occurring between 7:00 PM of the previous night and the current evening report.

These RM information reporting rules were put into place to reduce recall bias.

### **Abdominal Symptom Severity**

During the Evening Diary Report, the eDiary will capture separately the rating of abdominal pain, bloating, and discomfort experienced by the patient during the past 24 hours.

## **9.4.2 Handling of Missing eDiary Data**

In the eDiary, for each BM and rescue medicine use reported, the patient will be asked whether the BM or rescue medicine use occurred “today” or “yesterday.” The following conventions will be followed in the event of missing data:

### **Gaps in the eDiary Data**

If a patient does not complete either a spontaneous or evening report every day, there will be gaps in the data.

There will be no adjustments for these gaps in the eDiary data for the efficacy data analyses using an OC approach. Effectively, this means that analyses will assume that no rescue medicine use or BMs occurred during these gaps.

### **Missing “Today” or “Yesterday” Information for Rescue Medicine**

When a patient uses rescue medicine and the exact date of use is known, there will be a 2-day window during which any BMs will not be assessed as SBMs: (1) the day when the rescue medicine was administered and (2) the day after. If, in the daily diary, a patient has reported taking a rescue medicine but the corresponding date is missing, the rescue medicine use must have occurred either on the day of the diary entry or on the day before the diary entry. The rescue medicine window in this missing-date scenario will be 3 days, covering the day before the eDiary report, the day of the eDiary report, and the day after the eDiary report. This window will be used to determine if a BM should be considered an SBM.

For the analysis of rescue medicines, the missing date will be imputed as the date in which the rescue medicine was reported.

### **Missing “Today” or “Yesterday” Information for Bowel Movements**

If a patient reports having had a BM but does not provide the exact date, the BM must have occurred either on the day of the report or on the day before the report. For determining whether

a BM is an SBM, this 2-day window will be used in conjunction with the rescue medicine window. If there is any overlap between the BM window and the patient's rescue medicine window, the BM will not be considered an SBM.

Many analyses require specific dates for each BM. If a BM date is missing, it will be imputed as the date/time stamp of the eDiary report in which the BM was reported. However, the following exception applies to this imputation rule:

When the first day of the BM window is the last day of a rescue medicine window and the second day of the BM window is not also a day of a rescue medicine window, the missing BM date will be imputed as the first day of the BM window (i.e., the day before the eDiary report in which the BM was recorded). This rule of exception is designed to minimize the risk of mischaracterizing a non-spontaneous BM as an SBM.

### **Missing Stool Consistency Questions**

No imputation will be performed for a missing BSFS score or the stool consistency 5 point ordinal measure.

### **Missing Completeness of Evacuation Response**

If the completeness of evacuation response (Question #12) is missing, an SBM will not be considered complete.

### **Missing Daily Abdominal Symptoms**

No imputation will be performed for missing daily symptoms (Abdominal Pain, Abdominal Discomfort, Abdominal Bloating).

### **9.4.3 Weekly Stool Frequency Rates**

The components for calculating a patient's stool frequency rates (BM, SBM, and CSBM weekly rates) for a given analysis week are as follows:

- The number of BMs that occurred during that analysis week
- The number of those BMs that were SBMs
- The number of those SBMs that were CSBMs
- The length of time of the analysis week
- The determination of the length of time of an analysis week is provided in Section [9.4.3.1](#).

#### **9.4.3.1 Length of an Analysis Week**

With respect to a patient's scheduled analysis weeks, the term *duration* is used. In regard to the *duration* of a week, it is expected that 1 or more of a patient's "weeks" may not be exactly 7×24 hours in duration (e.g., a patient may withdraw or discontinue early from the trial). Deviations from the 7×24-hour norm are structural in nature; and, as such, the calculations of the weekly rates of SBMs or CSBMs will incorporate the actual duration of the week.

Following an observed-cases approach, no adjustment to the duration of a week will be made for missing eDiary data absent because of missed reports.

#### **9.4.3.2 Weekly Stool Frequency Rate Calculations**

The weekly frequency rate for SBMs (CSBMs) will be based on the number of SBMs (CSBMs) occurring during that week, adjusting for differences in the duration of the week versus the 7×24-hour norm. A description of the corresponding formula is provided below.

Weekly stool frequency rates for each analysis week will be calculated as follows:

$$\text{Weekly Frequency Rate (Analysis Week}_i\text{)} = (7 \times 24) \times C_i/D_i$$

Where:

$i$  is an indicator of analysis week number (e.g.,  $i = -2, -1, 1, \dots, 12$ ),

$C_i$  is the number of events (SBMs or CSBMs) reported during analysis week  $i$ , and

$D_i$  is the duration (in hours) of analysis week  $i$ , from beginning to end (Table 6).

#### 9.4.3.3 Overall Weekly Stool Frequency Rate Calculations for Each Analysis Period

For each of the 2 analysis periods (Pretreatment and Treatment), the overall weekly stool frequency rates will be calculated in a manner similar to that for an individual week. The corresponding formulas are provided below.

Overall weekly stool frequency rates for each analysis period will be calculated as follows:

$$\text{Weekly Frequency Rate (Analysis Period}_j\text{)} = (7 \times 24) \times C_j/D_j$$

Where:

$j$  is an indicator of analysis period number (e.g.,  $j = 1$  [pretreatment],  $2$  [treatment]),

$C_j$  is the number of events (SBMs or CSBMs) reported during analysis period  $j$ , and

$D_j$  is the duration (in hours) of analysis period  $j$ , from beginning to end (Table 6).

#### 9.4.4 Other Weekly Scores Derivation

For Abdominal Pain, Bloating, and Discomfort, the patient's weekly average will be the average of the non-missing daily scores reported by the patient during each week.

For stool consistency questions, the patient's weekly score will be the average of the non-missing daily scores from the SBMs reported by the patient during each week.

For straining, the patient's weekly straining score will be the average of the non-missing daily straining scores from the SBMs reported by the patient during each week.

For the abdominal symptom composite score, first the daily average of Abdominal Pain, Abdominal Bloating and Abdominal Discomfort will be calculated. If more than 1 of the symptom scores is missing on a day, that daily abdominal symptom composite score will be missing. Weekly scores will be based on the average of the non-missing abdominal symptom composite scores.

## **9.5 REPEATED OR UNSCHEDULED ASSESSMENTS OF SAFETY PARAMETERS**

If a patient has repeated assessments prior to the start of double-blind study drug, then the results from the final non-missing assessment made prior to the start of the double-blind study drug will be used as baseline. If end-of-study assessments are repeated or if unscheduled visits occur, the last non-missing post baseline assessment will be used as the end-of-study assessment for generating summary statistics. However, all post-baseline assessments will be used for PCS value determination as described above and all assessments will be presented in the data listings.

## **9.6 MISSING DATE OF THE LAST DOSE OF STUDY DRUG**

When the date of the last dose of double-blind study drug is missing for a patient in the Safety Population, all efforts should be made to obtain the date from the Investigator. If after all efforts are made it is still missing, the last eDiary entry will be used as the last dose date.

## **9.7 MISSING SEVERITY ASSESSMENT FOR ADVERSE EVENTS**

If severity is missing for an AE started prior to the first double blind study drug, all efforts should be made to obtain the severity from the investigator. If it is still missing after all efforts, then a severity of "Mild" will be assigned. If the severity is missing for an AE started on or after the date of the first dose of double-blind study drug, then a severity of "Severe" will be assigned. The imputed values for the missing severity assessment will be used for the incidence summary, while the actual missing values will be presented in data listings.

## **9.8 MISSING RELATIONSHIP TO STUDY DRUG FOR ADVERSE EVENTS**

If the relationship to study drug is missing for an AE started on or after the date of the first dose of double-blind study drug, all efforts should be made to obtain the date from the investigator. If it is still missing after all efforts, a causality of “Related” will be assigned in the corresponding analysis derived data set. The imputed values for the missing relationship to double-blind study drug will be used only for incidence summary, while the actual missing values will be presented in data listings.

